10.7.2.2. Handling of Missing Dates

| Element | Reporting Detail |
|---------|---|
| General | 
 Completely missing start or end dates will remain missing, with no imputation applied. Consequently, time to onset and duration of such events will be missing. |

10.7.2.3. Handling of Partial Dates

| Element | Reporting Detail |
|-------------------------|--|
| Concomitant Medications | 
 Partial dates for any concomitant medications recorded in the CRF will be imputed using the following convention: 
 If the partial date is a start date, a '01' will be used for the day and 'Jan' will be used for the month If the partial date is a stop date, a '28/29/30/31' will be used for the day (dependent on the month and year) and 'Dec' will be used for the month. The recorded partial date will be displayed in listings. |
| Adverse Events | 
 Any partial dates for adverse events will be raised to data management. If the full date cannot be ascertained, the following assumptions will be made: 
 If the partial date is a start date, a '01' will be used for the day and 'Jan' will be used for the month. |

| Element | Reporting Detail |
|---------|--|
| | 
 ○ However, if these results in a date prior to Week 1 Day 1 and the event could possibly have occurred during treatment from the partial information, then the Week 1 Day 1 date will be assumed to be the start date. ○ The AE will then be considered to start on-treatment (worst case). ○ If the partial date is a stop date, a '28/29/30/31' will be used for the day (dependent on the month and year) and 'Dec' will be used for the month, unless this is after the stop date of study treatment; in this case the study treatment stop date will be used. ● The recorded partial date will be displayed in listings. |

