6.3.11. Time Period and Frequency of Detecting AEs and SAEs

- AEs and SAEs will be collected from the start of Study Treatment until the follow-up contact at the timepoints specified in the Time and Events Table. (China sites should follow Section 11.1, [Appendix 1](#))
- Medical occurrences that begin prior to the start of study treatment but after obtaining informed consent may be recorded on the Medical History/Current Medical Conditions section of the CRF.
- Any SAEs assessed as related to study participation (e.g., protocol-mandated procedures, invasive tests, or change in existing therapy) or related to a GSK product will be recorded from the time a subject consents to participate in the study up to and including any follow-up contact. (China sites should follow Section 11.1, [Appendix 1](#))
- All SAEs will be recorded and reported to GSK within 24 hours as indicated in Section [6.3.12](#).
- Investigators are not obligated to actively seek AEs or SAEs in former study subjects. However, if the investigator learns of any SAE, including a death, at any time after a subject has been discharged from the study, and he/she considers the event reasonably related to the study treatment or study participation, the investigator must promptly notify GSK.

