10.4.2.2. Treatment States for AE Data

| Treatment State | Definition |
|--|---|
| Pre-Treatment | AE Start Date < Study Treatment Start Date |
| On-Treatment | Study Treatment Start Date ≤ AE Start Date ≤ Study Treatment Stop +1 |
| Post-Treatment | AE Start Date > Study Treatment Stop Date+1 |
| Onset Time Since 1 st Dose (Days) | If Treatment Start Date > AE Onset Date = AE Onset Date - Treatment Start Date If Treatment Start Date ≤ AE Onset Date = AE Onset Date - Treatment Start Date +1 Missing otherwise. |

| Treatment State | Definition |
|-----------------|--|
| Duration (Days) | AE Resolution Date – AE Onset Date + 1 |
| Drug-related | If relationship is marked 'YES' on Inform/CRF OR value is missing. |

NOTES:

- If the study treatment stop date is missing then the AE will be considered to be On-Treatment.
- If the AE onset date is missing or partial then the AE will be considered on-treatment unless there is evidence to the contrary (e.g. the month of the onset date is present and is less than the month of the first dose of study treatment).
- AEs reported by subjects who did not receive treatment will be considered pre-treatment.
- Any SAEs for screen failures, run-in failures or subjects who were randomised but did not receive treatment will be classified as pre-treatment SAEs.

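### For adverse events whose stop date stays partial after query, the cap at treatment stop gives post-treatment events an end before their onset and shortens events that outlast treatment

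*SAP*

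**What the plan says.** SAP 10.7.2.3 (Adverse Events) sends partial AE dates to data management first. Its imputation applies only to what remains: "If the full date cannot be ascertained, the following assumptions will be made". A partial stop date is completed to the last day of the recorded month, or to the end of December if the month is unknown, "unless this is after the stop date of study treatment; in this case the study treatment stop date will be used".

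The surrounding provisions are:

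- SAP 10.7.2.2: "Completely missing start or end dates will remain missing, with no imputation applied".
- SAP 10.4.2.2 defines AE duration as "AE Resolution Date – AE Onset Date + 1".
- The same section classes an AE as on-treatment if "Study Treatment Start Date ≤ AE Start Date ≤ Study Treatment Stop +1" and as post-treatment if "AE Start Date > Study Treatment Stop Date+1".
- Protocol 6.3.11: "AEs and SAEs will be collected from the start of Study Treatment until the follow-up contact". Protocol 4.9 places that contact 7 ± 2 days after Visit 9 or the Early Withdrawal visit.
- SAP 10.14.8 plans separate displays of post-treatment AEs (Table 3.6) and post-treatment non-fatal serious AEs (Table 3.18).

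**The concern.** The plan expects AEs that begin after the last dose and gives them their own class and tables. Yet it forbids any imputed stop date later than the last dose. For those AEs the two rules cannot both give a sensible answer. The same cap cuts short an AE that began on treatment and resolved afterwards. Events that lead to stopping treatment are plausible examples: under the liver criteria in Protocol 6.3.4, product is withdrawn at once and monitoring continues until the values settle.

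The neighbouring rules suggest an oversight. In the same section, the AE start-date rule is adjusted according to what the partial information allows. The concomitant-medication stop-date rule uses month or year end with no cap at treatment stop. Only the AE stop-date rule has a cap and no check of plausibility.

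At stake is the correctness of two derived variables in the safety data: the imputed end date and the duration.

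**Working it through.** The plan states no figure to reproduce, so the check applies the rule directly.

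**Notation.** T = treatment stop date; O = AE onset; S = true resolution date; E = last day of the recorded month (31 December if only the year is known). The imputed end is min(E, T), so the derived duration is min(E, T) − O + 1. The recorded month or year contains S, so E ≥ S.

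**(a) Onset after treatment stop, O = T + k with k ≥ 1.** Here E ≥ S ≥ O > T, so the cap always applies:

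duration = T − (T + k) + 1 = 1 − k.

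| Onset | Derived duration (days) |
|---|---|
| T+1 (still classed on-treatment) | 0 |
| T+2 | −1 |
| T+4 | −3 |
| T+10 | −9 |

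With last dose Day 168 and onset Day 172, 168 − 172 + 1 = −3. The last row comes from the visit schedule: Visit 9 is T+1 when the last dose is taken at Visit 8, and the contact follows 5 to 9 days later, at T+6 to T+10. That assumption limits only the size of the negative value. In withdrawn subjects the gap may be longer.

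**(b) Onset on or before treatment stop, true resolution after it, O ≤ T < S.** Again E ≥ S > T, so the cap always applies:

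duration = T − O + 1, against a true S − O + 1, a shortfall of S − T days.

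- Onset 8 September, T = 10 September, true stop 5 October recorded only as October: derived 3 days, true 28. The imputed end of 10 September contradicts the recorded month.
- Onset 1 February, T = 20 February, stop recorded only as March (non-leap year): derived 20 days. The true value lies between 29 (1 March) and 59 (31 March).

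Enumeration over every T in one year, onset from T−30 to T and resolution from T+1 to T+60, with month known and unknown, gives too short a duration in all 365 × 31 × 60 × 2 = 1,357,800 combinations.

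**(c) True resolution on or before treatment stop, S ≤ T.** Now min(E, T) ≥ S, so the derived duration is never too short. With onset 1 February, true stop 10 February, T = 15 February and stop recorded as February, the cap gives 15 days, month end would give 28, and the truth is 10. Here the cap reduces an overstatement.

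**The case against.** The strongest reply is that little depends on this rule, and most of that reply stands.

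- **Scope.** A reader might infer that the SAP caps all AE stop dates. It does not. Complete dates are used as recorded and fully missing dates stay missing. Only partial dates that survive a query, and whose completed value falls after treatment stop, are changed.
- **Direction.** A reader might infer that the rule always makes events look shorter. Case (c) shows otherwise: when the event ended by treatment stop, the cap leaves the duration correct or too long. The downward error is certain only for events that outlast treatment.
- **Consequence.** A reader might infer that the safety conclusions, including those on serious AEs, are affected. The documents do not support that. Classification uses onset only, so incidence tables do not change. SAP 10.14.8 lists no summary of AE duration. The duration summary described in the notes to SAP Table 5 concerns COPD exacerbations, which have their own derivation in SAP 10.4.2.3. Listings show the partial date as recorded. Serious AEs are also described in narratives (Protocol 8.3.5.2). A derived duration might appear in an AE listing, but those layouts are not in the documents.

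The reply does not remove the defect. The SAP defines AE duration and states a rule that gives it impossible values.

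**Conclusion.** The rule is wrong as written, with minor consequences. Every AE with onset after treatment stop and an unresolved partial stop date receives an end before its onset, with duration 1 − k days for onset k days after treatment stop. Every AE with onset by treatment stop, true resolution after it and an unresolved partial stop date is shortened by the number of days it outlasted treatment. These results assume only that the recorded month or year is correct and that the onset used is the one in the analysis data.

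The number of affected records cannot be derived from the documents. It is probably small, because each one needs a stop date still partial after query and a completed date after the last dose. The efficacy analyses do not use this rule.

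**What to change.** Add one sentence to SAP 10.7.2.3: the imputed AE stop date may not be earlier than the later of the AE onset date and the first day of the recorded month or year. If an upper bound is kept, make it the last study contact date instead of the treatment stop date, and state that the lower bound prevails if the two conflict.

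Two of the cases above show the effect:

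- T = 10 September, onset 14 September, stop recorded as September (true stop 17 September, 4 days). The current rule gives −3. With no upper bound, the end is 30 September and the duration 17. With a last contact assumed on 20 September (T+10), it is 20 − 14 + 1 = 7.
- Onset 1 February, T = 20 February, stop recorded as March. With a last contact assumed on 27 February (T+7), the two bounds conflict, the lower one prevails, and the end is 1 March: 29 days, consistent with the recorded month.

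The cost is that sentence and a small change to the derivation code. Durations for these few records may be overstated, as is usual with month-end imputation, but they can no longer be impossible. No incidence table or classification changes.

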10.7.2.4. Handling of Missing Data for Statistical Analysis

| Element | Reporting Detail |
|------------------------------|--|
| MMRM | 
 ● Missing data will not be directly imputed in this analysis; however, all non-missing data for a subject will be used within the analysis to estimate the treatment effect |
| ANCOVA | 
 ● For analysis of trough FEV1 at Day 169, sensitivity analyses with LOCF to imputed missing data will be produced for supportive analysis. ● Missing data will not be imputed for other analysis. |
| Cox's proportional Analysis | 
 ● Missing data will not be imputed. |
| Logistic regression Analysis | 
 ● Missing data will not be imputed. |

10.8. Appendix 8: Values of Potential Clinical Importance**10.8.1. Laboratory Values**

Threshold values for liver function test results, which are considered values of potential clinical importance, are:

- 3 times the upper limit of normal (ULN) for Alanine Aminotransferase (ALT)
- 2 times the ULN for Total Bilirubin (BILT).

Graphical displays of liver function test results will be produced as described in Section 8.2 (Clinical Laboratory Analyses) to identify any results above the thresholds.

Laboratory values will be flagged relative to the normal range. Clinical concern ranges will not be used.

10.8.2. ECG

Clinical concern ranges will not be used.

10.8.3. Vital Signs

Clinical concern ranges will not be used.

10.9. Appendix 9: Multicenter Studies

This study was randomized centrally within country. No strata were defined.

Country will be considered a fixed effect in all analyses on overall population. For primary efficacy analysis, interaction with treatment will be explored by fitting a model with an additional treatment by country interaction term; any interaction found to be statistically significant at the 10 % level will be further investigated and characterised. Center will not be included as a covariate in China subgroup statistical analyses.

All results will be produced for all countries combined. In addition, summary statistics of demography, screening lung function, primary and secondary endpoints will be produced by country.

10.10. Appendix 10: Examination of Covariates, Subgroups & Other Strata

The details of covariates that will be used in statistical analyses have been clarified in Section 7.1 (Primary Statistical Analyses), Section 7.2 (Secondary Statistical Analyses) and Section 7.3 (Other Statistical Analyses).

Consistency of treatment effect across covariates fitted in the primary efficacy endpoint analysis models will be examined by fitting separate models to examine treatment by baseline, treatment by country (not done for China alone sub-group analysis) and treatment by smoking status at screening interactions. Separate analysis models will also be fitted to examine treatment by ICS use, treatment by reversibility to salbutamol and treatment by percent predicted FEV₁.

No formal statistical analysis of sub-groups of the study population for either the overall analysis or the China subgroup analysis will be performed.

10.11. Appendix 11: Multiple Comparisons & Multiplicity

There is no adjustment for multiplicity to be applied in this study for the analysis on all countries overall as there is only one primary endpoint (Clinic visit trough (pre-bronchodilator) FEV1 on Treatment Day 169) and only one primary comparison (UMEC62.5 mcg vs. placebo) of interest. Treatment comparisons for secondary and other endpoints will be considered exploratory.

For China subgroup analysis, as the China subgroup analysis is powered, the inference on the primary endpoint on China subgroup is dependent on statistical significance having been achieved for the primary endpoint on the analysis on all countries overall. Treatment comparisons for secondary and other endpoints in China subgroup analysis will also be considered exploratory.

10.12. Appendix 12: Model Checking and Diagnostics for Statistical Analyses

10.12.1. Statistical Analysis Assumptions

| | |
|-------------|---|
| Endpoint(s) | 
 • Trough FEV1 • Trough FVC • TDI Focal Score • Serial FEV1 • Serial FVC |
| Analysis | 
 • MMRM 
 ○ The Kenward and Roger method (KR) for approximating the denominator degrees of freedom and correcting for bias in the estimated variance-covariance of the fixed effects will be used. 
 ○ In the event the model fails to run using the KR method, then the residual method will be used instead. ○ Distributional assumptions underlying the model used for analysis will be examined by obtaining a normal probability plot of the residuals and a plot of the residuals versus the fitted values (i.e. checking the normality assumption and constant variance assumption of the model respectively) to gain confidence that the model assumptions are reasonable. |

| | |
|-------------|---|
| Endpoint(s) | 
 • 0-6 h weighted mean FEV1 on Day 1 • Mean number of puffs of rescue medication per day over each treatment period • Pulse rate • Systolic • Diastolic blood pressure • QTc(F) • PR interval • Heart rate |
| Analysis | 
 • ANCOVA 
Distributional assumptions underlying the model used for analysis will be examined by obtaining a normal probability plot of the residuals and a plot of the residuals versus the fitted values (i.e. checking the normality assumption and constant variance assumption of the model respectively) to gain confidence that the model assumptions are reasonable.
 |

| | |
|-------------|---|
| Endpoint(s) | 
 • Time to Onset (an increase of 100mL in FEV1 above baseline) during 0-6 h post-dose on Day 1 • Time to First COPD Exacerbation |
| Analysis | 
 • Cox's proportional hazards model 
The proportional hazards assumption for this method of analysis will be examined by obtaining the Kaplan-Meier estimates of the survival function $S(t)$ over time separately for treatment group. Under the assumption of proportional hazard between the treatment
 |

groups, $\ln\{-\ln[S(t)]\}$ for the two groups should be parallel to each other and the distance between them constant. If the curves are approximately parallel, then the proportional hazard assumption is not violated. If these curves cross each other or diverge greatly from the assumption of parallel lines, then the assumption is not met.

| | |
|--------------------|--|
| Endpoint(s) | 
• Proportion Achieving Increase in FEV1 of $\geq 12\%$ and ≥ 200 mL above Baseline at any Time During 0-6 h Post-dose on Day 1• Proportion Achieving Increase of ≥ 100 mL above Baseline in Trough FEV1• Proportion of Responders According to TDI Focal Score |
| Analysis | 
• Logistic regression model• Computation of confidence intervals for the odds ratios is based on the individual Wald tests.• BUD/FOR will be used as the reference level for treatment• Goodness-of-fit of the logistic model will be examined using the LACKFIT option for the model statement in SAS. Index plots of the Pearson residuals and deviance criteria residuals will be plotted by using the IPLOTS option for the model statement in SAS. |

10.13. Appendix 13 – Abbreviations & Trade Marks

10.13.1. Abbreviations

| Abbreviation | Description |
|--------------|--|
| AE | Adverse Event |
| AIC | Akaike's Information Criteria |
| A&R | Analysis and Reporting |
| CI | Confidence Interval |
| CPMS | Clinical Pharmacology Modelling & Simulation |
| CS | Clinical Statistics |
| CSR | Clinical Study Report |
| CTR | Clinical Trial Register |
| DOB | Date of Birth |
| DP | Decimal Places |
| eCRF | Electronic Case Record Form |
| IA | Interim Analysis |
| ICH | International Conference on Harmonisation |
| IDSL | Integrated Data Standards Library |
| IMMS | International Modules Management System |
| IP | Investigational Product |
| ITT | Intent-To-Treat |
| GUI | Guidance |
| MMRM | Mixed Model Repeated Measures |
| PCI | Potential Clinical Importance |
| PD | Pharmacodynamic |
| PDMP | Protocol Deviation Management Plan |
| PK | Pharmacokinetic |
| PP | Per Protocol |
| QC | Quality Control |
| QTcF | Frederica's QT Interval Corrected for Heart Rate |
| QTcB | Bazett's QT Interval Corrected for Heart Rate |
| RAP | Reporting & Analysis Plan |
| RAMOS | Randomization & Medication Ordering System |
| SAC | Statistical Analysis Complete |
| SOP | Standard Operation Procedure |
| TA | Therapeutic Area |
| TFL | Tables, Figures & Listings |
| GSK | GlaxoSmithKline |

10.13.2. Trademarks

| Trademarks of the GlaxoSmithKline Group of Companies | Trademarks not owned by the GlaxoSmithKline Group of Companies |
|--|--|
| HARP | SAS |
| RAMOS | S-PLUS |
| RANDALL | |

10.14. Appendix 14: List of Data Displays

10.14.1. Data Display Numbering

The following numbering will be applied for RAP generated displays:

| Section | Tables | Figures |
|--|-------------|-------------|
| Study Population (Overall Analysis) | 1.1 to 1.37 | 1.1 to 1.1 |
| Study Population (China Subgroup Analysis) | 1.1 to 1.35 | 1.1 to 1.1 |
| Efficacy(Overall Analysis) | 2.1 to 2.56 | 2.1 to 2.21 |
| Efficacy (China Subgroup Analysis) | 2.1 to 2.49 | 2.1 to 2.21 |
| Safety (Overall Analysis) | 3.1 to 3.48 | 3.1 to 3.17 |
| Safety (China Subgroup Analysis) | 3.1 to 3.48 | 3.1 to 3.17 |
| Section | Listings | |
| ICH Listings | 1 to 25 | |
| Other Listings | 26 to 54 | |

10.14.2. Mock Example Shell Referencing

Non IDSL specifications will be referenced as indicated and if required an example mock-up displays provided in [Appendix 15: Example Mock Shells for Data Displays](#).

| Section | Figure | Table | Listing |
|----------|--------|-------|---------|
| Efficacy | NA | NA | EFF_L1 |

NOTES:

- Non-Standard displays are indicated in the 'IDSL / TST ID / Example Shell' or 'Programming Notes' column as '[Non-Standard] + Reference.'

10.14.3. Deliverable [Priority]

| Delivery [Priority] ^[1] | Description |
|------------------------------------|-------------------------------------|
| SAC [1] | Final Statistical Analysis Complete |

NOTES:

- Indicates priority (i.e. order) in which displays will be generated for the reporting effort.

10.14.4. Study Population Tables

| Study Population Tables | | | | | | |
|-------------------------|--------------------|---------------------------|-------------------------------|--|---|------------------------|
| IMCT No. | China Subgroup No. | Population | IDSL / TST ID / Example Shell | Title | Programming Notes | Deliverable [Priority] |
| 1.1. | 1.1. | All Subjects Enrolled | DB2114634 5.01 | Summary of Subject Populations | | SAC |
| 1.2. | 1.2. | Modified ITT | DB2114634 5.09 | Summary of Exclusions from the Per Protocol Analysis | | SAC |
| 1.3. | 1.3. | Modified ITT | DB2114634 5.02 | Summary of Attendance at Each Clinic Visit | | SAC |
| 1.4. | 1.4. | Modified ITT | DB2114634 5.03 | Summary of Subject Disposition | | SAC[1] |
| 1.5. | 1.5. | Screen and Run-in Failure | DB2114634 5.04 | Summary of Reasons for Screen Failures | | SAC |
| 1.6. | 1.6. | Screen and Run-in Failure | DB2114634 5.05 | Summary of Reasons for Run-in Failures | | SAC |
| 1.7. | 1.7. | Modified ITT | DB2114634 5.06 | Summary of Number of Subjects by Country and Centre | For China subgroup, Country will be omitted from the title. | SAC |
| 1.8. | 1.8. | Screen and Run-in Failure | DB2114634 5.07 | Summary of Inclusion/Exclusion/Randomisation Criteria Deviations for Screen or Run-in Failures | | SAC |
| 1.9. | 1.9. | Modified ITT | DB2114634 5.08 | Summary of Inclusion/Exclusion/Randomisation Criteria Deviations for Modified Intent-to-treat Subjects | | SAC |

| Study Population Tables | | | | | | |
|-------------------------|--------------------|--------------|-------------------------------|---|--|------------------------|
| IMCT No. | China Subgroup No. | Population | IDSL / TST ID / Example Shell | Title | Programming Notes | Deliverable [Priority] |
| 1.10. | 1.10. | Modified ITT | DB2114634 5.09 | Summary of Important Protocol Deviations | Remove rows of Full Protocol Deviations, Partial Protocol Deviations and Time-point Specific Protocol Deviations and summarize all PDs with DVIMPFL marked as "Y". | SAC |
| 1.11. | 1.11. | Modified ITT | DB2114634 5.10 | Summary of Demographic Characteristics | | SAC[1] |
| 1.12. | NA | Modified ITT | DB2114634 5.11 | Summary of Demographic Characteristics by Country | | SAC |
| 1.13. | 1.12. | PP | DB2114634 5.12 | Summary of Demographic Characteristics | | SAC |
| 1.14. | 1.13. | Modified ITT | DB2114634 5.13 | Summary of Race and Racial Combinations | | SAC |
